5.3. Screen Failures

Screen failures are defined as participants who consent to participate in the clinical study but are not subsequently randomized to study intervention. A minimal set of screen failure information is required to ensure transparent reporting of screen failure participants to meet the Consolidated Standards of Reporting Trials (CONSORT) publishing requirements and to respond to queries from regulatory authorities. Minimal information includes demography, reason(s) for screen failure, eligibility criteria, and any study-procedure related SAEs.

Individuals whose ALT, AST, bilirubin, creatinine clearance, or eGFR results initially do not meet the criteria for participation in this study may have the test(s) repeated one time within 10 days; if the repeat value is not exclusionary, the participant may be eligible for enrollment and randomization.

6. STUDY INTERVENTION

Study intervention is defined as any investigational intervention, marketed products, or placebo intended to be administered to a study participant according to the study protocol.

6.1. Study Intervention(s) Administered

Induction and consolidation treatments are administered as *cycles*. A complete treatment cycle consists of the administration of therapy (i.e., chemotherapy with cytarabine ± anthracycline plus blinded study intervention) and all scheduled assessments to evaluate the response to treatment, including bone marrow and hematologic recovery.

Details of dociparstat solution for injection are listed in [Table 3](#) and standard of care chemotherapy agents are listed in [Table 4](#). Details of the dosing regimens for each treatment cycle (and age group) are presented in [Table 5](#).

Table 3: Dociparstat Details

Intervention Name	Dociparstat sodium
Type	Drug
Dose Formulation	Solution for injection
Unit Dose Strength(s)	50 mg/mL
Route of Administration	Intravenous infusion (bolus followed by continuous infusion)
Use	Experimental agent
IMP or Non-IMP	Investigational medicinal product (IMP)
Sourcing	Provided centrally by the sponsor
Packaging and Labeling	Provided in 10-mL vials (1 vial per kit). Each kit and vial will be labeled in accordance with applicable regulatory requirements.
Current/ Former Names	Dociparstat sodium; 2-O, 3-O desulfated heparin; ODSH; DSTAT; CX-01

Normal saline (sodium chloride 0.9%) will be used to dilute dociparstat solution for injection before each infusion. In order to maintain blinding of randomized study intervention, normal saline will also be used as the de facto placebo. Commercially-available product will be purchased and provided (sourced) locally by the study site (or subsidiary or designee); packaging and labeling will be per local requirements for commercial products.

Table 4: Standard of Care Therapy Details

Group Name	Standard of Care for the Dociparstat and Placebo Groups (cytarabine + an anthracycline will be administered to all participants)		
Intervention Name	Cytarabine	Idarubicin ^a	Daunorubicin ^a
Type	Drug	Drug	Drug
Dose Formulation	Solution for injection		
Unit Dose Strength(s)	Refer to product label		
Route of Administration	IV infusion		
Use	Standard of care chemotherapy		
IMP or Non-IMP	Non-investigational medicinal product (NIMP)		
Sourcing	Provided locally by the study site, subsidiary, or designee		
Packaging and Labeling	Commercial product packaging and labeling		
Current/ Former Names ^b	Ara-C, DepoCyt, cytosine arabinoside, cytarbel, Cytosar, aracytidine, Aracytin, arbaine, 1-beta-d-arabinofuranosylcytosine	Idamycin, Idaru, Zavedos	Cerubidine, daunomycin, rubidomycin, rubomycin C, daunorrubicina leukaemomycin C

^a The use of idarubicin versus daunorubicin is at the discretion of the investigator based on standard institutional practice.

^b List is not exhaustive of all product names available in all countries.

Dociparstat sodium solution for injection is supplied as 1-vial kits. Calculate dosing based on participant weight and prepare/dilute the drug product before IV infusion. Dociparstat must be administered via a dedicated infusion line. Do not mix with other IV medications.

Dociparstat is administered as an initial IV bolus dose over 5 minutes, immediately followed by a continuous IV infusion 24 hours daily for 5 or 7 days (see [Table 5](#)). Dociparstat is intended for use in combination with standard chemotherapy (i.e., dociparstat should not be used as monotherapy).

Table 5: Dosing Regimen for Induction and Consolidation Therapy

	Standard of Care / Background Chemotherapy	Study Intervention
Induction cycle – all participants and Reinduction cycle (as indicated) – participants 18 to 59 years	
All participants will receive an initial induction cycle:
 
 • Cytarabine 100 mg/m²/day via continuous IV infusion 24 hours daily for 7 days (Day 1 to Day 8) AND • Anthracycline once daily for 3 days (on Day 1, Day 2, and Day 3): 
 ◦ Idarubicin 12 mg/m² by slow (10 to 15 minutes) IV injection OR ◦ Daunorubicin 60 mg/m² via rapidly flowing IV infusion 
Note: FLT3-positive participants may receive cytarabine 200 mg/m²/day.
 
When reinduction is indicated, participants 18 to 59 years will receive the same dosing schedule.
	
 • Dociparstat 4 mg/kg or placebo IV bolus on Day 1, administered 30 minutes after completion of the first dose of idarubicin or daunorubicin, followed by • Dociparstat 0.25 mg/kg/hr or placebo by continuous IV infusion for 24 hours daily for 7 days (starting on Day 1 and ending on Day 8 [168 hours])
Reinduction cycle (as indicated) – participants ≥60 years	
When reinduction is indicated, participants ≥60 years will receive a modified dosing schedule:
 
 • Cytarabine 100 mg/m²/day via continuous IV infusion for 5 days AND • Anthracycline on Day 1 and Day 2: 
 ◦ Idarubicin 12 mg/m² by slow (10 to 15 minutes) IV injection OR ◦ Daunorubicin 60 mg/m² given via rapidly flowing IV infusion 
Note: FLT3-positive participants may receive cytarabine 200 mg/m²/day
	
 • Dociparstat 4 mg/kg or placebo IV bolus on Day 1, administered 30 minutes after completion of the first dose of idarubicin or daunorubicin, followed by • Dociparstat 0.25 mg/kg/hr or placebo by continuous IV infusion for 24 hours daily for 5 days (starting on Day 1 and ending on Day 6 [120 hours])
Consolidation cycles (up to 4 cycles, as applicable)	
Only participants with a documented response (CR or CRi) are eligible for consolidation.
 
 • Cytarabine via IV infusion over 3 hours, administered twice daily (at 12-hour intervals) on Day 1, Day 3, and Day 5 
 ◦ Age 18-59 years: 3 g/m²/dose ◦ Age ≥60 years: 1.5 g/m²/dose 	
 • Dociparstat 4 mg/kg or placebo IV bolus on Day 1, administered 30 minutes after completion of the first dose of cytarabine, followed by • Dociparstat 0.25 mg/kg/hr or placebo by continuous IV infusion for 24 hours daily for 5 days (starting on Day 1 and ending on Day 6 [120 hours])

Note: Participants with a FLT3 mutation may also receive treatment with midostaurin at the investigator's discretion and dependent on local availability.

6.2. Preparation, Handling, Storage, and Accountability

6.2.1. Dose Preparation

Dosing will be calculated on the basis of each participant's weight for study intervention and body surface area for chemotherapy (cytarabine, daunorubicin, and idarubicin). It is recommended that the dosing calculations and preparation of each dose of study intervention be confirmed by a second unblinded pharmacist.

Preparation of randomized study intervention (i.e., dociparstat or placebo) will be performed by an unblinded pharmacist within the investigational pharmacy. The pharmacist will prepare study intervention to the appropriate calculated dose. Normal saline will be used to dilute the IV bolus dose and continuous maintenance infusion of dociparstat. The dociparstat IV bolus dose will be diluted to a total infusion volume of 30 mL. The 24-hour continuous infusion will have the appropriate volume of dociparstat added to approximately 250 mL or 500 mL of 0.9% normal saline.

The placebo IV bolus dose will be a total infusion volume of 30 mL of 0.9% normal saline only. Placebo for the continuous infusion will be 250 mL or 500 mL of 0.9% normal saline only.

Only participants randomized in the study may receive study intervention and only authorized site staff may prepare, supply, or administer study intervention.

All study intervention syringes and bags need to be blinded (masked) after final preparation and prior to leaving the pharmacy. Sites will follow their own labeling procedures to identify prepared study intervention (i.e., dociparstat or placebo) for each participant in a blinded manner.

Refer to the product labels for information on preparation and administration of cytarabine, daunorubicin, and idarubicin.

6.2.2. Handling, Storage, and Accountability

A sufficient quantity of vials of dociparstat solution for injection will be supplied to the investigator (or qualified designee) at each study center. Once received at the study center, kits of dociparstat should be stored in accordance with the labeled storage conditions, in a securely locked area, with access limited to the unblinded pharmacist and authorized site staff.

[**Note:** The labeled storage conditions are dependent on the manufactured drug product batch/lot.]

The investigator or qualified designee (e.g., unblinded pharmacist) must confirm appropriate temperature conditions have been maintained during transit for all study intervention received and must report and resolve any discrepancies before use of the study intervention.

The investigator or qualified designee (e.g., unblinded pharmacist) is responsible for ensuring adequate accountability of all used and unused study intervention. This includes acknowledgment of receipt of the shipment(s) of study intervention (date, quantity, condition, and vial numbers), participant dispensing records (date, participant number, and vial number), and returned or destroyed vials. All study intervention records must be maintained at the site and copies must be submitted to Chimerix at the end of the study. The unblinded investigator designee should promptly inform the unblinded study monitor of any discrepancies in accountability of study intervention.

After verification of the study intervention records by the unblinded study monitor, all remaining study intervention supplies should be destroyed according to directions provided by Chimerix (or its designee) and/or any applicable site-specific standard operating procedures. If necessary, unused study intervention supplies may be returned to the appropriate depot with prior approval from Chimerix (or its designee). If study intervention is destroyed on site, the investigator must maintain accurate records for all study intervention destroyed. Records must show the identification and quantity of each unit destroyed, the method of destruction, and person who disposed of the drug.

Refer to the product labels for information on handling and storage of normal saline, cytarabine, daunorubicin, idarubicin, and ancillary supplies (e.g., IV bags and tubing).

6.3. Dose Modification

All participants randomized into the study will be treated with an initial induction cycle of blinded study intervention plus standard 7+3 chemotherapy starting on Day 1. The total number of treatment cycles administered to each participant is determined by the investigator through evaluations of treatment response, potential toxicity or tolerability issues, and suitability for alternate treatments (e.g., HCT).

There are no modifications in the mg/kg dosing of blinded study intervention. Criteria for interruption and discontinuation of study intervention are provided in Section 7.

6.4. Measures to Minimize Bias: Randomization and Blinding

A randomized, double-blind, placebo-controlled study design was selected as the most robust design to minimize potential bias.

Participants who meet all applicable eligibility criteria will be centrally randomized to one of two study intervention groups (dociparstat or placebo) in a 1:1 ratio using an automated IRT system and a computer-generated randomization code provided by the sponsor or designee.

Randomization will be stratified based upon FLT3 status (FLT3+ vs FLT3-), genetic risk (intermediate vs adverse), and age (<65 years vs ≥65 years).

Once a randomization number has been assigned, it will not be re-assigned to any other participant in the study. The IRT system will also be used to track study intervention dispensing.

Investigators, participants, and sponsor personnel (to the extent practicable) will be blinded to each participant's assigned study intervention throughout the course of the study. In order to maintain this blind, an otherwise uninvolved third party (an unblinded study pharmacist) will be responsible for the preparation and dispensation of blinded study interventions (i.e., dociparstat and placebo) and will ensure that there are no differences in appearance or time taken to dispense study intervention following randomization.

In the event of a regulatory inspection or quality assurance audit, the auditor(s) will be allowed access to unblinded study intervention records at the site(s) to verify that randomization and dispensing have been done accurately. Additional roles and responsibilities that require unblinding of specified sponsor (and/or designated contract research organization) personnel not directly involved in the conduct of the study include supply chain, regulatory reporting of expedited safety reports, and data monitoring committee (DMC) reviews.

Normal saline (sodium chloride 0.9%) will be used as the study intervention placebo for both the loading doses and the continuous infusions. Placebo-controlled studies are the gold standard for clinical trials, as they reduce bias in care and conduct during the study. Though the efficacy endpoints are objective, safety assessments are less biased when treatment allocation is masked. Most importantly, downstream decisions regarding postinduction therapy are best made without knowledge of initial treatment assignment to reduce possible bias in this study.

Modest effects of dociparstat on aPTT have been observed in previous studies. Although the Phase 2b mean aPTT values during the continuous infusion were nominally higher for dociparstat 0.25 mg/kg than control, the individual participant values were variable and had considerable overlap between groups; therefore, individual aPTT measurements are not expected to unblind the participant's treatment assignment. In this Phase 3 study, potential unblinding will be mitigated by obtaining initial aPTT measurements no sooner than 8 hours after the IV bolus (after the time of peak effect) and by instructions to obtain blood for aPTT measurements from a location that is separate from the dociparstat infusion. Specifically, blood should be obtained via separate venipuncture and/or a catheter separate from the one used to administer study intervention. If the specimen is drawn from a heparinized line, first draw 5 mL of blood from the line for discard before drawing the aPTT sample.

Emergency unblinding: The IRT system will be used for blind-breaking instructions. In case of an emergency, the investigator has the sole responsibility for determining if unblinding of a participant's intervention assignment is warranted. Participant safety must always be the first consideration in making such a determination. If the investigator decides that unblinding is warranted, the investigator should make every effort to contact the sponsor prior to unblinding a participant's intervention assignment unless this could delay emergency treatment. If a participant's intervention assignment is unblinded, the sponsor must be notified within 24 hours after breaking the blind. The date and reason that the blind was broken must be recorded in the source documentation and electronic case report form (eCRF), as applicable.

6.5. Study Intervention Compliance

Participants will receive study intervention and standard of care chemotherapy directly from the investigator or qualified designee, under medical supervision. The date and start/stop times of each dose of study intervention and standard of care chemotherapy administered will be recorded in the source documents and in the eCRF.

Study participant identification and dose of study intervention will be confirmed at the time of dosing by a member of the site staff other than the person administering the study intervention.

6.6. Concomitant Therapy

Information about the participant's concomitant medications/therapies will be collected in the eCRF as specified below.

Collection time periods:

- Prior medications: All medications taken from 30 days prior to the time of signing the informed consent form (ICF) through the time of randomization.

- Concomitant medications: All medications and transfusions from the time of first dose of study intervention on Day 1 through 42 days after the start of the last treatment cycle (induction, reinduction, or consolidation, whichever is later).
- Follow-up: Only AML therapies (i.e., for the treatment of AML and/or prevention of relapse) from 43 days after start of last treatment cycle through the time of last study follow-up.

Information to collect:

- Names (nonproprietary names are preferred) for all prescription medications and growth factors, and details of transfusions (do not need to collect use of vitamins, supplements, or IV fluids).
- Reason for use (indication).
- Start and end dates of administration.
- Dosage information, including dose, units, route, and frequency.

Contact the medical monitor (or designee) if there are any questions regarding concomitant or prior therapy.

6.6.1. Prohibited Therapies

Refer to the exclusion criteria (see Section 5.2) for medications prohibited prior to randomization (and the associated time period) in the study.

The following medications are prohibited throughout the duration of the treatment period (i.e., during protocol-specified induction and consolidation treatment cycles, unless otherwise specified):

- AML treatments not specified in the protocol, including (but not limited to) the following:
 - Vyxeos (daunorubicin and cytarabine liposome for injection)
 - Myelotarg (gemtuzumab ozogamicin)
 - Venetoclax
 - Decitabine or azacitidine
 - Isocitrate dehydrogenase (IDH) inhibitors (e.g., Tibsovo [ivosidenib], Idhifa [enasidenib])
 - Mitoxantrone
- Hematopoietic growth factors during induction and reinduction cycles.
- Anticoagulants (e.g., unfractionated heparin, low molecular weight heparin, warfarin, factor Xa inhibitors) [If a participant requires short-term anticoagulant therapy, see Section 7.1]. Heparin flush of indwelling catheters is permitted. Discuss use of other agents for catheter occlusion with the medical monitor.
- Investigational agents.

6.6.2. Permitted Therapies

The following medications are permitted during the study:

- Midostaurin: Participants who are known to have a FLT3 mutation may, at the investigator's discretion and dependent on local availability, receive midostaurin in accordance with the product label.
- Infection prophylaxis and treatment, and transfusion support – according to institutional standard of care.
- Granulocyte colony-stimulating factor (G-CSF) following consolidation therapy.

If used, recommended treatment is a single dose (per package labeling) of peg-filgrastim/liposomal G-CSF (Neulasta or biosimilar) administered subcutaneously 24 to 48 hours after the last dose of cytarabine consolidation in participants who have achieved an MRD_{neg} CR or CRi after induction/reinduction. Alternatively, other G-CSF agents may be used after consolidation therapy per institutional standard of care and package labeling.

6.7. Intervention after the End of the Study

Dociparstat is intended for use as up-front treatment in combination with standard induction and consolidation chemotherapy in participants with newly-diagnosed AML. Since dociparstat is not intended for continued maintenance treatment, the study intervention will not be provided beyond the protocol-specified treatment period.

After the end of the treatment period, the participants' ongoing medical care and treatment in the event of a recurrence will be the responsibility of the participants' physician(s).

7. DISCONTINUATION OF STUDY INTERVENTION AND PARTICIPANT DISCONTINUATION/WITHDRAWAL

7.1. Interruption of Study Intervention

Infusion of study intervention (i.e., dociparstat or placebo) will be interrupted in the following situations:

aPTT: Participants with aPTT >45 seconds will have repeat testing performed as soon as practicable. If aPTT is confirmed >45 seconds, interrupt the study intervention infusion. To minimize time that the participant is off therapy, perform repeat testing for aPTT approximately 2 to 6 hours after interruption (as practicable). Infusion may be resumed once aPTT is <35 seconds. **Note:** samples are not to be obtained from the same line as study intervention infusion (e.g., collect via peripheral venipuncture).

Grade 3 or higher hemorrhagic AEs: Study intervention infusion will be interrupted for Grade 3 or higher hemorrhagic AEs in the setting of aPTT >40 seconds, or Grade 3 or higher hemorrhagic AEs that are deemed to be related to study intervention, regardless of aPTT. Study intervention infusion may be resumed once the participant is determined to be stable and the aPTT is <35 seconds.

Note: Grade 3 or higher hemorrhagic AEs are also considered AEs of special interest.

Renal function: If the calculated creatinine clearance drops below 30 mL/min or eGFR drops below 30 mL/min/1.73 m² prior to or during dosing with study intervention, the infusion will be held until the creatinine clearance or eGFR rises to ≥ 30 .

Electrocardiogram (ECG)/QTc: Study intervention infusion will be interrupted if a participant meets any of the following criteria (based on the average of triplicate ECG readings; see Section 8.3.3 for details about QTc correction formulas):

- Without underlying bundle branch block:
 - Interrupt for QTc >500 msec OR uncorrected QT >600 msec,
- With underlying bundle branch block:
 - If baseline QTc <450 msec, then interrupt for QTc >500 msec
 - If baseline QTc 450 to 480 msec, then interrupt for QTc >530 msec

In the event of prolonged QTc, the participant should also be assessed for other medications that may impact QT interval (see [Appendix 6: Drugs Known to Prolong the QT Interval](#)), with any necessary changes made to concomitant medications. Infusion of study intervention may be resumed once QTc is <480 msec. Following resumption of infusion, ECGs are to be checked daily until the participant has had 3 consecutive (daily) tracings with QTc <480 msec, after which follow-up ECGs will be as per institutional standard of care. Report any new, clinically-relevant finding as an AE.

Bilirubin: If total bilirubin is >2 mg/dL, refer to the daunorubicin/idarubicin product label for dosage adjustments. No adjustment to the study intervention dosing is recommended.

Anticoagulant therapy: If a participant requires short-term anticoagulant therapy, interrupt the administration of study intervention. Infusions may be resumed if anticoagulant therapy is discontinued and aPTT is <35 seconds.

Note: If study intervention is interrupted and not restarted during the same treatment cycle, the participant may receive study intervention (bolus and infusion) during the next treatment cycle (assuming the participant no longer meets any of the interruption criteria).

Reasons for dose interruption will be entered into the eCRF. The total daily volume of IV solution infused (obtained directly from the IV pump data) will be recorded in the comment section of the eCRF for each participant who requires dose interruption.

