14. History of severe congestive heart failure or other cardiac disease that contraindicates the use of idarubicin or daunorubicin (e.g., cardiac ejection fraction $<45\%$, as determined by echocardiography or multigated acquisition scan).

Diagnostic assessments:

15. QTc >480 msec (see Section 8.3.3 for details about QTc correction formulas).
16. Severe renal impairment, as determined by calculated creatinine clearance <30 mL/min or estimated glomerular filtration rate (eGFR) <30 mL/min/1.73 m².
17. Alanine aminotransferase (ALT) or aspartate aminotransferase (AST) >3 x upper limit of normal (ULN) or total bilirubin >2 x ULN.

Other:

18. Woman of childbearing potential who is pregnant, breastfeeding, and/or not using a highly effective method of contraception (consistent with local regulations regarding the methods of contraception for those participating in clinical studies).
19. History of allergy or hypersensitivity to heparin, pork, or any excipients in the dociparstat formulation.
20. Any other condition, including abnormal laboratory values, that, in the judgement of the investigator, could put the participant at increased risk or interfere with the conduct or planned analyses of the study.

Intervention Groups and Duration: All participants will receive treatment with an initial cycle of standard intensive induction chemotherapy (i.e., cytarabine plus either idarubicin or daunorubicin “7+3” treatment regimen) in combination with randomized study intervention (i.e., dociparstat or placebo). Participants may also receive a reinduction cycle if bone marrow at Day 14 to 23 shows persistent disease, and up to 4 cycles of consolidation chemotherapy. The specific visit schedule and number of cycles of treatment will be dependent on institutional standard practice and each participant’s individual response to treatment.

Study intervention dosing is calculated based on weight and chemotherapy dosing is calculated based on body surface area.

	Standard of Care / Background Chemotherapy	Study Intervention

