7.2. Discontinuation of Study Intervention

In some instances, it may be necessary for a participant to permanently discontinue study intervention. Reasons for permanent discontinuation of study intervention may include the following:

- Participant did not achieve CR/CRi at the end of the reinduction treatment cycle.
- Criteria for restarting study intervention after interruption were not met.
- Treatment-related AE of unacceptable severity.
- Participant requests to discontinue study intervention.
- Investigator determines discontinuation is in the best interests of the participant for safety, behavioral, compliance, administrative, or other reasons.

Participants who discontinue study intervention early will complete the early discontinuation assessments (refer to the Schedule of Activities/Assessments; Section 1.2) and will continue to be followed-up for outcomes in the long-term follow-up period of the study until death or for 5 years after randomization.

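### Minor wording gap in 7.1: after a QTc hold that was not restarted, the next-cycle Note literally allows re-dosing at up to 500 msec (530 in one subgroup), although a held infusion may resume only below 480 msec

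*Combined protocol and SAP*

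**What the plan says.** Section 7.1 has three provisions that bear on QTc, and the synopsis repeats them.

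- **Hold.** Without bundle branch block: "Interrupt for QTc >500 msec OR uncorrected QT >600 msec". With bundle branch block, the limit is 500 msec if baseline QTc is below 450. Otherwise: "If baseline QTc 450 to 480 msec, then interrupt for QTc >530 msec". The criteria are assessed "based on the average of triplicate ECG readings".
- **Resume.** "Infusion of study intervention may be resumed once QTc is <480 msec". After that: "Following resumption of infusion, ECGs are to be checked daily until the participant has had 3 consecutive (daily) tracings with QTc <480 msec".
- **Next cycle.** A Note covers an infusion that was interrupted and not restarted in the same cycle. The participant may receive bolus and infusion in the next cycle, "assuming the participant no longer meets any of the interruption criteria". The Note applies to every hold reason and does not mention the resumption limits.

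Three other places matter. Exclusion 15 (Section 5.2 and synopsis) bars entry at QTc above 480 msec. Section 7.2 gives, among reasons that may lead to permanent discontinuation, "Criteria for restarting study intervention after interruption were not met". Section 8.3.3 and Table 1 schedule ECGs for the initial induction cycle only, and Table 2 has no ECG row; 8.3.3 also allows additional readings when Section 7 calls for them.

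**The concern.** The Note is the only sentence that deals directly with next-cycle dosing after a hold that was not restarted, and it points to the hold limits instead of the resumption limits. A participant whose QTc has already passed 500 (or 530) msec on study intervention could then be given a fresh 4 mg/kg bolus plus infusion at, say, 490 msec. At that value 7.1 would not let the held infusion be switched back on. The looser limit thus governs the larger exposure.

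It looks more like an oversight than a choice. The Amendment 1 rationale in Appendix 9 says the 7.1 resumption limit was moved to 480 msec to match Exclusion 15, and the Note was not tied to that limit. Two things are at stake: caution on re-exposure in a few previously held participants, and consistent dosing decisions across approximately 120 centers.

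**Working it through.** The plan gives no figure to reproduce. The check compares thresholds and then bounds the number of participants.

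**Step 1. Turn the Note into QTc limits.** Being clear of the interruption criteria is the complement of the hold rules in 7.1.

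| Participant | Hold if QTc | Next-cycle dosing allowed by the Note | Held infusion may resume | Literal gap |
|---|---|---|---|---|
| No bundle branch block | >500 (or uncorrected QT >600) | ≤500, and uncorrected QT ≤600 | <480 | 500 − 480 = 20 msec |
| Bundle branch block, baseline <450 | >500 | ≤500 | <480 | 500 − 480 = 20 msec |
| Bundle branch block, baseline 450 to 480 | >530 | ≤530 | <480 | 530 − 480 = 50 msec |

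**Step 2. Ask whether other text closes the gap.**

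- The resumption sentence is not expressly confined to one cycle, so a site could carry 480 forward. But it speaks of resuming an infusion, and a new bolus and infusion in a later cycle is not clearly that. The renal rule in 7.1 expressly covers values found before dosing; the QTc rule does not.
- Section 7.2 lists unmet restart criteria only as a possible reason for stopping permanently, while the Note expressly contemplates dosing after a hold that was not restarted. The two are left unreconciled.
- Section 8.3 has the investigator discuss immediate safety concerns with the sponsor. That permits a stricter decision without setting a limit.

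**Step 3. Scheduled checks.** Later cycles: 1 reinduction + up to 4 consolidation = up to 5, with 0 scheduled ECGs. Applying the Note after a QTc hold therefore rests on unscheduled tracings.

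**Step 4. Number affected.** The documents give no hold rate, so all four rates below are assumptions, applied to 570 randomized participants:

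- held for QTc: 0.5% to 3%
- not restarted in that cycle: 10% to 50%
- goes on to another cycle: 50% to 80%
- QTc then inside the gap: 10% to 30%

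Low: 570 × 0.005 × 0.10 × 0.50 × 0.10 = 0.014. 
Midpoints: 570 × 0.0175 × 0.30 × 0.65 × 0.20 = 0.39. 
High: 570 × 0.03 × 0.50 × 0.80 × 0.30 = 2.05.

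That is about 0 to 2 participants. With 1:1 randomization and equal hold rates in both arms, half would be on saline, leaving about 0.01 to 1 exposed to dociparstat.

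Low hold rates are plausible. Of the two scheduled tracings after dosing starts (end of bolus on Day 1, end of infusion on Day 8), only the first comes early enough to trigger a hold.

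**The case against.** The strongest reply is that the rest of the protocol already handles this. A QTc hold usually goes unrestarted because QTc did not fall below 480 msec before the infusion period ended, and 7.2 names that situation as a ground for stopping. The Note permits dosing but does not oblige it, and the investigator and sponsor can both intervene. The next cycle also starts later, after any QT-prolonging medication has been reviewed, so a different limit could be deliberate. All of this reduces the practical risk. It does not settle which limit applies, because the only text written for this situation names the hold criteria.

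A reader might infer that 480 msec is the protocol's general ceiling for giving study intervention and that the Note breaches it. The documents do not support that. An infusion that was never held may run up to 500 or 530 msec by design, and a participant with no hold needs no QTc check before reinduction or consolidation. Exclusion 15 governs entry, and the 480 in 8.3.3 only prompts a repeat tracing. The relevant comparison is with the resumption rule.

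A reader might also infer a demonstrated cardiac hazard. The risk table in 2.3.1 lists only bleeding for dociparstat, and nothing in the documents reports a QT effect. The investigator's brochure was not available.

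Finally, the aPTT rule has the same structure: hold above 45 seconds, resume below 35. Bleeding is the documented risk, so a clause that repaired only QTc could suggest that the aPTT limit lapses at the next cycle. That objection stands and shapes the fix.

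**Conclusion.** The inconsistency is real but minor. Taken literally, the Note allows re-dosing after an unrestarted QTc hold in a range where 7.1 would not let the held infusion resume: from 480 up to 500 msec, or up to 530 msec with bundle branch block and a baseline of 450 to 480. Without bundle branch block, uncorrected QT must also be no more than 600 msec. Other sections allow a site to use 480 but do not require it.

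The estimate of about 0 to 2 participants rests entirely on the four assumed rates. OS, EFS, alpha and power are untouched. The QT/QTc endpoint is a per-participant proportion, and someone already held for QTc would already count in it, provided its criteria are no stricter than the hold limits. With so few affected and no QT signal in the documents, this is a clarification to consider at the next amendment, not a required correction.

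**What to change.** In the Note, in both 7.1 and the synopsis, keep the existing condition ("assuming the participant no longer meets any of the interruption criteria") and extend it inside the parenthesis with:

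*and meets the resumption criterion stated above for the reason the infusion was held; for a QTc hold, QTc <480 msec on a predose ECG in the next cycle*

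Tying the clause to the reason for the hold keeps the aPTT limit of below 35 seconds and the other resumption limits in force. The renal rule does not change in effect, since hold and resumption share the value 30. Tables 1 and 2 and Section 8.3.3 need no edit, because 8.3.3 already provides for additional readings.

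The cost is a few extra ECGs and an occasional previously held participant who misses study intervention in a later cycle. Examples are a participant with bundle branch block and a baseline near 480 msec, or one held for aPTT whose usual value is 35 seconds or more.
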